3.4.2.2 Secondary Efficacy Variable

Secondary efficacy variables are as follows:

- The **Eczema Area and Severity Index (EASI)** will be assessed at each visit, except screening visit. It quantifies the severity of a subject's atopic dermatitis based on both lesion severity and the percent of BSA affected.

Four anatomic sites – head, upper extremities, trunk, and lower extremities – are assessed for erythema, induration (papules), excoriation and lichenification as seen on the day of the examination. The severity of each sign is assessed using a 4-point scale: 0 = No symptoms, 1 = Slight, 2 = Moderate, 3 = Marked.

The area affected by atopic dermatitis within a given anatomic site is estimated as a percentage of the total area of that anatomic site and assigned a numerical value according to the degree of atopic dermatitis involvement as follows: 0 = no involvement, 1 = < 10 %, 2 = 10 to < 30%, 3 = 30 to < 50%, 4 = 50 to < 70%, 5 = 70 to < 90%, 6 = 90 to 100 %.

The EASI score is obtained by using the formula:

$$\begin{aligned} \text{EASI} = & 0.1 * (E_h + I_h + Ex_h + L_h) * A_h + \\ & 0.2 * (E_u + I_u + Ex_u + Ex_u) * A_u + \\ & 0.3 * (E_t + I_t + Ex_t + Ex_t) * A_t + \\ & 0.4 * (E_l + I_l + Ex_l + Ex_l) * A_l \end{aligned}$$

Where E, I, Ex, L and A denote erythema, induration, excoriation, lichenification and area, respectively, and h, u, t, and l denote head, upper extremities, trunk, and lower extremities, respectively. The EASI score ranges from 0 (no disease) - 72 (maximal disease). The score will be set to missing in case of at least one missing value.

The change from baseline in EASI at Week 2, Week 4, Week 8, and Week 10 will be calculated as the value at the visit minus the value at Baseline. Percent change from baseline will also be calculated. In addition, change and percent change from Week 8 to Week 10 will be calculated.

- The overall **Body Surface Area (BSA)** affected by AD will be evaluated (from 0 to 100%) at each visit. One patient's palm represents 1% of his/her total BSA. For all study visits except at screening, the BSA of involved skin will be measured with the SCORAD measurement. The change from Baseline will be calculated as the value at the visit minus the value at Baseline. The change from baseline will be calculated at Week 2, Week 4, Week 8 and Week 10. Percent change from baseline will also be calculated. In addition, change and percent change from Week 8 to Week 10 will be calculated.

- The **SCORing Atopic Dermatitis (SCORAD)** will be measured at each visit, except the screening visit. The SCORAD grading system is a standard tool to assess the AD severity in clinical studies in Europe. Six items (erythema, edema/papulation, oozing/crusts, excoriation, lichenification, and dryness) are selected to evaluate the AD severity. The intensity of each item is graded using a 4-point scale: 0 = No symptoms, 1 = Mild, 2 = Moderate, 3 = Severe.

The area chosen for grading must be representative (average intensity) for each item. The individual intensity ratings for each item will then be added (ranging from 0-18) and multiplied by 3.5, giving a maximal score of 63.

The overall BSA affected by AD is evaluated (from 0 to 100%) and divided by 5. One patient's palm represents 1% of his/her total BSA. The maximum is 20.

Subjective items include loss of sleep and the occurrence of pruritus. These are evaluated by asking patients to indicate on the 10-cm scale (0-10) of the assessment form the point corresponding to the average value for the last three days/nights. The combined maximum score of these two is 20.

The sum of the above measures represents the SCORAD which can vary from 0 to 103. If the subjective scores of pruritus and loss of sleep are excluded, the SCORAD becomes objective SCORAD (score range 0-83).

The score will be set to missing if there is at least one missing value. The change from Baseline will be calculated as the value at the visit minus the value at Baseline. The change from baseline will be calculated at Week 2, Week 4, Week 8, and Week 10. Percent change from baseline will also be calculated. In addition, change and percent change from Week 8 to Week 10 will be calculated.

- The **Visual Analog Scale (VAS) of Pruritus** will be assessed with the SCORAD measurement for all study visits except screening. This will be evaluated by asking subjects to indicate on the 10-cm scale (0-10) of the assessment form the point corresponding to the average value for the last three days/nights. The change from Baseline will be calculated as the value at the visit minus the value at Baseline. The change from baseline will be calculated at Week 2, Week 4, Week 8, and Week 10. Percent change from baseline will also be calculated. In addition, change and percent change from Week 8 to Week 10 will be calculated.
- The **Patient-Oriented Eczema Measure (POEM)** will be assessed at each visit, except screening visit. The POEM is a self assessment of disease severity by the patient. The following questions are to be rated as: 0=No Days, 1=1-2 Days, 2=3-4 Days, 3=5-6 Days, 4=Everyday.

1. Over the last week, on how many days has your skin been itchy because of your eczema?
2. Over the last week, on how many nights has your sleep been disturbed because of your eczema?
3. Over the last week, on how many days has your skin been bleeding because of your eczema?
4. Over the last week, on how many days has your skin been weeping or oozing clear fluid because of your eczema?
5. Over the last week, on how many days has your skin been cracked because of your eczema?
6. Over the last week, on how many days has your skin been flaking off because of your eczema?
7. Over the last week, on how many days has your skin felt dry or rough because of your eczema?

The POEM score is the sum of the 7 question ratings for a possible total of 28 (more severe eczema). The score will be set to missing if there is at least one missing value. The change from Baseline will be calculated as the value at the visit minus the value at Baseline. The change from baseline will be calculated at Week 2, Week 4, Week 8, and Week 10. Percent change from baseline will also be calculated. In addition, change and percent change from Week 8 to Week 10 will be calculated

- The **Dermatology Life Quality Index (DLQI)** questionnaire is a simple 10-question validated questionnaire which will be completed at each visit, except screening. The following questions are to be assessed by the patient:

1.	Over the last week, how itchy, sore, painful or stinging has your skin been?	Very much (3) A lot (2) A little (1) Not at all (0)	
2.	Over the last week, how embarrassed or self conscious have you been because of your skin?	Very much (3) A lot (2) A little (1) Not at all (0)	
3.	Over the last week, how much has your skin interfered with you going shopping or looking after your home or yard ?	Very much (3) A lot (2) A little (1) Not at all	Not relevant (0)
4.	Over the last week, how much has your skin influenced the clothes you wear?	Very much (3) A lot (2) A little (1)	

		Not at all	Not relevant (0)
5.	Over the last week, how much has your skin affected any social or leisure activities?	Very much (3) A lot (2) A little (1) Not at all	Not relevant (0)
6.	Over the last week, how much has your skin made it difficult for you to do any sport ?	Very much (3) A lot (2) A little (1) Not at all	Not relevant (0)
7.	Over the last week, has your skin prevented you from working or studying ?	Yes (3) No (0)	
	If "No", over the last week how much has your skin been a problem at work or studying ?	A lot (2) A little (1) Not at all (0)	
8.	Over the last week, how much has your skin created problems with your partner or any of your close friends or relatives ?	Very much (3) A lot (2) A little (1) Not at all	Not relevant (0)
9.	Over the last week, how much has your skin caused any sexual difficulties ?	Very much (3) A lot (2) A little (1) Not at all	Not relevant (0)
10.	Over the last week, how much of a problem has the treatment for your skin been, for example by making your home messy, or by taking up time?	Very much (3) A lot (2) A little (1) Not at all	Not relevant (0)

The DLQI score is the sum of the 10 questions for a possible total of 30 (quality of life is impaired). 'Not relevant' and 'Unanswered' questions will be scored as 0. The change from Baseline will be calculated as the value at the visit minus the value at Baseline. The change from baseline will be calculated at Week 2, Week 4, Week 8, and Week 10. Percent change from baseline will also be calculated. In addition, change and percent change from Week 8 to Week 10 will be calculated

- **Trans epidemal Water Loss (TEWL)**, the clinical severity of AD and associated effect on skin barrier function will be evaluated at each visit, except the screening visit. This evaluation will be performed at selected sites that have demonstrated previous experience with this device.

At Baseline (Day 0), the investigator will select three representative areas of active AD for each subject; the location of these sites will be recorded. At subsequent visits, TEWL readings for each area of AD will be taken in standard room ambient conditions (22-25°C, 40-60% relative humidity); the mean of the TEWL measurements will be used for the

analyses. The change from Baseline will be calculated as the value at the visit minus the value at Baseline. The change from baseline will be calculated at Week 2, Week 4, Week 8, and Week 10. Percent change from baseline will also be calculated. In addition, change and percent change from Week 8 to Week 10 will be calculated.

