8 STUDY ASSESSMENTS

8.1 Efficacy Assessments

Clinical evaluations of atopic dermatitis will be performed by an experienced and qualified dermatologist (board certified or equivalent). To assure consistency and reduce variability, the same assessor should perform all assessments on a given subject whenever possible.

8.1.1 *Investigator's Global Assessment (IGA)*

The Investigator's Global Assessment (IGA) of Disease Severity (Appendix B) (25, 26) will be assessed at each visit. The IGA is a global assessment of the current state of the disease. It is a 6-point morphological assessment of overall disease severity and will be determined according to the following definitions: 0 (clear), 1 (almost clear), 2 (mild), 3 (moderate), 4 (severe) and 5 (very severe). In order to be eligible, subjects must have an IGA score ≥ 3 at Baseline visit (Day 0).

8.1.2 *Eczema Area and Severity Index (EASI)*

The Eczema Area and Severity Index (EASI) will be assessed at each visit, except screening visit. It quantifies the severity of a subject's atopic dermatitis based on both lesion severity and the percent of BSA affected (24). The EASI is a composite score ranging from 0-72 that takes into account the degree of erythema, induration/papulation, excoriation, and lichenification (each scored from 0 to 3 separately) for each of four body regions, with adjustment for the percent of BSA involved for each body region and for the proportion of the body region to the whole body. A detailed procedure of EASI score calculation is provided in Appendix C.

8.1.3 *Body Surface Area (BSA)*

The overall BSA affected by AD will be evaluated (from 0 to 100%) at each visit. One patient's palm represents 1% of his/her total BSA. For all study visits except at screening, the BSA of involved skin will be measured with the SCORAD measurement (see below for description) and evaluated as a separate endpoint. In order to be eligible, subjects must have a BSA of at least 10% at Baseline visit (Day 0).

8.1.4 *SCORing Atopic Dermatitis (SCORAD)*

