15.2 Ethical Review

It is the understanding of the Sponsor that this protocol (and any amendment) as well as appropriate consent procedures, will be reviewed and approved by a research ethics board/institutional review board (REB/IRB). This Board must operate in accordance with the current Federal regulations. A letter or certification of approval will be sent by the Investigator to the Sponsor prior to initiation of the study, and also whenever subsequent modifications to the protocol are made.

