19 APPENDIX B – INVESTIGATOR'S GLOBAL ASSESSMENT

Score	Grade	Definition
0	Clear	No evidence of disease with the exception of residual pigment changes and/or xerosis
1	Almost clear	Perceptible erythema, papulation/infiltration
2	Mild	Mild erythema, papulation/infiltration
3	Moderate	Moderate erythema, papulation/infiltration
4	Severe	Severe erythema, papulation/infiltration
5	Very Severe	Severe erythema, papulation/infiltration with oozing/crusting

20 APPENDIX C - Eczema Area and Severity Index (EASI)

Four anatomic sites – head, upper extremities, trunk and lower extremities – are assessed for erythema, induration (papules), excoriation and lichenification as seen on the day of the examination. The severity of each sign is assessed using a 4-point scale:

- 0 = No symptoms
- 1 = Slight
- 2 = Moderate
- 3 = Marked

The area affected by atopic dermatitis within a given anatomic site is estimated as a percentage of the total area of that anatomic site and assigned a numerical value according to the degree of atopic dermatitis involvement as follows:

- 0 = no involvement
- 1 = < 10 %
- 2 = 10 to < 30%
- 3 = 30 to < 50%
- 4 = 50 to < 70%
- 5 = 70 to < 90%
- 6 = 90 to 100 %

The EASI score is obtained by using the formula

$$\text{EASI} = 0.1 (E_h + I_h + Ex_h + L_h) A_h + 0.2 (E_u + I_u + Ex_u + Ex_u) A_u + 0.3 (E_t + I_t + Ex_t + Ex_t) A_t + 0.4 (E_l + I_l + Ex_l + Ex_l) A_l$$

Where E, I, Ex, L and A denote erythema, induration, excoriation, lichenification and area, respectively, and h, u, t, and l denote head, upper extremities, trunk, and lower extremities, respectively.

21 APPENDIX D - SCORing Atopic Dermatitis (SCORAD)

Six items (erythema, edema/papulation, oozing/crusts, excoriation, lichenification, and dryness) are selected to evaluate the AD severity. The intensity of each item is graded using a 4-point scale:

- 0 = No symptoms
- 1 = Mild
- 2 = Moderate
- 3 = Severe

The area chosen for grading must be representative (average intensity) for each item. The individual intensity ratings for each item will then be added (ranging from 0-18) and multiplied by 3.5, giving a maximal score of 63.

The overall BSA affected by AD is evaluated (from 0 to 100%) and divided by 5. One patient's palm represents 1% of his/her total BSA. The maximum is 20.

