7.2 Secondary Efficacy Analyses

The second efficacy endpoints are:

- Change from baseline in IGA at week 2, 4, and 8
- Change from baseline in EASI at week 2, 4, and 8
- Change from baseline in POEM at week 2, 4, and 8
- Change from baseline in DLQI at week 2, 4, and 8
- Change from baseline in SCORAD at week 2, 4, and 8
- Change from baseline in VAS at week 2, 4, and 8
- Change from baseline in BSA at week 2, 4, and 8
- Proportion of patients achieving at least 1-point decrease in IGA at Week 8

All secondary endpoint based on the change from baseline will be assessed using an ANCOVA where the change from baseline will be the dependant variable and including the treatment group and site as fixed effects and baseline value as a covariate. In addition, ANCOVA will also be performed on the change from baseline at week 10 and on the change from Week 8 to Week 10.

All secondary endpoint based on categories will be analysed using a Cochran-Mantel-Haenszel test stratified by site and the p-value from this test will be presented along with frequency and percentage of subjects for each category.

All change and percent change values will be summarized using descriptive statistics, for each treatment group and visit. Proportion of subjects with no, 1-point, 2-point, 3-point, decrease/increase, will be presented at Week 8.

All statistical analyses will be done at each visit and using the ITT (primary analysis) and PP (supportive analysis) population. All the analyses will be done using observed values. Results collected during the early termination visit related to Week 8 and Week 10 will not be included. No sensitivity analysis will be done for missing values.

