Eczema Area and Severity Index
(Enrolled Subjects)

Excoriation							
Treatment Group	Site ID	Subject ID	Visit	Head	Upper Extremities	Trunk	Lower Extremities

Program: L16_2_6_2.SAS, Generated on DDMMYY HH:MM

Lisintg 16.2.6.2 (Part 4)
Eczema Area and Severity Index
(Enrolled Subjects)

Lichenification								
Treatment Group	Site ID	Subject ID	Visit	Head	Upper Extremities	Trunk	Lower Extremities	EASI Score

Program: L16_2_6_2.SAS, Generated on DDMMYY HH:MM

Lisintg 16.2.6.3
Patient-Oriented Eczema Measure
(Enrolled Subjects)

Treatment Group	Site ID	Subject ID	Visit	Q1	Q2	Q3	Q4	Q5	Q6	Q7	POEM Score
-----------------	---------	------------	-------	----	----	----	----	----	----	----	------------

Program: L16_2_6_3.SAS, Generated on DDMMYY HH:MM

Lisintg 16.2.6.4 (Part 1)
Dermatology Quality of Life Index
(Enrolled Subjects)

Treatment Group	Site ID	Subject ID	Visit	Q1	Q2	Q3	Q4	Q5	Q6
-----------------	---------	------------	-------	----	----	----	----	----	----

Program: L16_2_6_4.SAS, Generated on DDMMYY HH:MM

Lisintg 16.2.6.4 (Part 2)
Dermatology Quality of Life Index
(Enrolled Subjects)

Treatment Group	Site ID	Subject ID	Visit	Q7	Q7A	Q8	Q9	Q10	DLQI Score
-----------------	---------	------------	-------	----	-----	----	----	-----	------------

Program: L16_2_6_4.SAS, Generated on DDMMYY HH:MM

Lisintg 16.2.6.5 (Part 1)
SCORing Atopic Dermatitis
(Enrolled Subjects)

Treatment Group	Site ID	Subject ID	Visit	Erythema Intensity	Edema/Papulation Intensity	Oozing/Crust Intensity	Excoriation Intensity	Lichenification Intensity	Dryness Intensity	Total Intensity
-----------------	---------	------------	-------	-----------------------	-------------------------------	---------------------------	--------------------------	------------------------------	----------------------	--------------------

Program: L16_2_6_5.SAS, Generated on DDMMYY HH:MM

Lisintg 16.2.6.5 (Part 2)
SCORing Atopic Dermatitis
(Enrolled Subjects)

Treatment Group	Site ID	Subject ID	Visit	Extent Area involved (BSA)	Pruritus VAS Symptom Score	Sleep loss VAS Symptom Score	Objective SCORAD	SCORAD
-----------------	---------	------------	-------	-------------------------------	-------------------------------	---------------------------------	---------------------	--------

Program: L16_2_6_5.SAS, Generated on DDMMYY HH:MM

Lisintg 16.2.6.6
Trans Epithelial Water Loss
(Enrolled Subjects)

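### The printed EASI formula drops lichenification and counts excoriation twice in three of the four body regions, contradicting the plan's own definition of the score

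*SAP*

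**What the plan says.** SAP section 3.4.2.2 states that the head, upper extremities, trunk and lower extremities "are assessed for erythema, induration (papules), excoriation and lichenification as seen on the day of the examination". Each sign is graded 0 to 3 and each region's area 0 to 6. It then says "The EASI score is obtained by using the formula" and prints four weighted terms. The head term (weight 0.1) adds erythema, induration, excoriation and lichenification. The upper-extremity term is "0.2 * (E_u + I_u + Ex_u + Ex_u) * A_u". The trunk (0.3) and lower-extremity (0.4) terms have the same form, with excoriation entered twice and lichenification absent. The legend below defines L as lichenification and gives the score range as 0 to 72.

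Protocol Appendix C, to which protocol section 8.1.2 refers for the calculation, has the same pattern: "0.2 (E_u + I_u + Ex_u + Ex_u) A_u" for the upper extremities, and likewise for the trunk and lower extremities. Section 8.1.2 itself says that the score "takes into account the degree of erythema, induration/papulation, excoriation, and lichenification (each scored from 0 to 3 separately) for each of four body regions". The last part of mock Listing 16.2.6.2 in SAP section 13.2 has lichenification columns for all four regions next to the EASI score.

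SAP section 7.2 lists "Change from baseline in EASI at week 2, 4, and 8" among the secondary endpoints. It also applies the ANCOVA to the change at Week 10 and to the change from Week 8 to Week 10, in both the ITT and PP populations.

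**The concern.** The formula and the definition cannot both be right. The text requires lichenification to count in every region; the formula uses it only in the head, which has the smallest weight. Because the SAP presents the formula as the way the score is obtained, a programmer who follows it exactly will produce a different instrument from the one described. That derived score would feed every EASI summary, ANCOVA, table and figure.

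Routine checks are poorly placed to catch this. The range is the same under both versions. Any patient whose excoriation and lichenification grades agree outside the head gets the same score either way. Two programmers working independently from the same text would agree on the same wrong value.

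The missing-item rule also becomes unclear. The SAP sets the score to missing if any value is missing, but under the printed formula a missing lichenification grade outside the head is not an input at all.

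**Working it through.** **Inputs.** Regional weights are 0.1, 0.2, 0.3 and 0.4 for head (h), upper extremities (u), trunk (t) and lower extremities (l). Signs run from 0 to 3 and area scores from 0 to 6. All come from SAP 3.4.2.2 and protocol Appendix C.

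**Two versions of the score.**
- By definition: the sum over all four regions of weight × (E + I + Ex + L) × A.
- As printed: the same for the head, but weight × (E + I + Ex + Ex) × A for u, t and l.

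**Stated range.** With all signs 3 and all areas 6, each version gives (0.1 + 0.2 + 0.3 + 0.4) × 12 × 6 = 72. The stated 0 to 72 is reproduced under both, so it does not tell them apart.

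**Error per score (printed minus definition).**
0.2(Ex_u − L_u)A_u + 0.3(Ex_t − L_t)A_t + 0.4(Ex_l − L_l)A_l

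The affected weight is 0.2 + 0.3 + 0.4 = 0.9. The bound is 0.9 × 3 × 6 = 16.2 points in either direction. A one-point gap between excoriation and lichenification in all three regions shifts the score by 0.9 × area score: 0.9 at area 1, 2.7 at area 3, 5.4 at area 6.

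**Largest possible contribution of each sign.**
- By definition, excoriation and lichenification can each supply 1.0 × 3 × 6 = 18.0 points.
- As printed, excoriation can supply 0.1 × 3 × 6 + 0.9 × 6 × 6 = 1.8 + 32.4 = 34.2 points, and lichenification 0.1 × 3 × 6 = 1.8.

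**Illustrations.** The sign profiles are assumptions, not trial data. Each is (E, I, Ex, L), the same in all regions, with area score 3.

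| Profile | By definition | As printed |
|---|---|---|
| (1,1,0,3) | 15.0 | 6.9 |
| (1,1,3,0) | 15.0 | 23.1 |
| (2,2,2,2) | 24.0 | 24.0 |

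For the first row, the definition gives 5 × 3 = 15.0. The printed formula gives 0.1 × 5 × 3 + 0.9 × 2 × 3 = 1.5 + 5.4 = 6.9.

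| Change from baseline | By definition | As printed |
|---|---|---|
| (2,2,2,3) to (2,2,2,1) | −6.0 | −0.6 |
| (2,2,1,3) to (1,1,1,1) | −12.0 | −6.6 |
| (2,2,2,3) to (1,1,0,3) | −12.0 | −17.4 |
| (2,2,2,3) to (1,1,1,2) | −12.0 | −12.0 |

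The last row agrees because the gap between excoriation and lichenification is the same at both visits, so the error cancels. A change is misstated only when the weighted gap outside the head differs between visits.

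**The case against.** The strongest reply is that this is a misprint whose intent is obvious. The text on either side of the formula, the legend, the head term, protocol 8.1.2 and the mock listing all point to four signs in four regions. A programmer with three unused lichenification inputs has good reason to ask. The documents contain no program, so harm to the analysis is conditional on literal coding. EASI is one of eight secondary efficacy endpoints in a phase IIa trial, and no testing hierarchy depends on it. Lichenification is collected in every region, so the score can be recomputed from the item data at any time. The 16.2-point bound needs extreme and opposite grades with near-total involvement of all three regions, and some plausible profiles show no error. Finally, the fault might lie in how the PDF was read rather than in the document.

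Much of this stands as a limit on the consequence: the effect is conditional, it is confined to a secondary endpoint, it can be repaired, and its typical size is unknown. None of it removes the defect. The cues to the correct form are the same passages that the formula contradicts, and nothing in either document corrects it. A programmer who silently fixed it would leave an analysis that departs from the written SAP. The mock EASI listing has no area-score column, so a reader could not recompute the score from it and notice. A reading fault is unlikely, because the same three terms are affected in two differently laid-out formulas while the head term is intact. The SAP was probably copied from the protocol, however, so the two are not independent evidence, and a look at the source PDFs is worthwhile.

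**Conclusion.** The concern holds. The EASI formula is wrong as printed in both documents: it omits lichenification and doubles excoriation in regions with 0.9 of the weight, against the plan's own definition. That conclusion rests on the text alone and is certain, apart from the small chance of a PDF reading fault.

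The size depends on data the documents do not give. Per score, the error is bounded by 16.2 points either way and is zero when excoriation and lichenification agree outside the head or the weighted differences cancel. The direction and size of any bias between arms cannot be stated, and an effect on the reported results requires that the formula was programmed literally. The IGA primary endpoint and the sample size are not affected. Because this is the operative scoring rule for a listed secondary endpoint, it must be corrected.

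**What to change.** 1. In SAP 3.4.2.2, replace the second Ex_u, Ex_t and Ex_l with L_u, L_t and L_l. This also settles which items the missing-value rule covers.
2. Before database lock, test the EASI program on a case where excoriation and lichenification differ outside the head. With (E, I, Ex, L) = (1,1,0,3) and area score 3 in all regions it must return 15.0, not 6.9. If lock has already passed, recompute EASI from the item-level data and compare.
3. Make the same three replacements in protocol Appendix C.

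The first two steps are enough to protect the analysis. Until the third is done, the departure from Appendix C can be recorded in SAP section 11.

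The cost is six symbols, three in each document, and one test case. No new assessments are needed, because lichenification is already scored in all four regions. The protocol correction goes through ethics review: section 15.2 requires a letter or certification of approval "whenever subsequent modifications to the protocol are made".

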3.2 Secondary Endpoints

- Change from baseline in IGA at week 2, 4 and 8.
- Change from baseline in EASI (Eczema Area and Severity Index) at week 2, 4 and 8.
- Proportion of patients achieving at least a 1-point decrease in IGA at week 8.
- Change from baseline in the Patient Orientated Eczema Measure (POEM) at week 2, 4 and 8.
- Change from baseline in the Dermatology Life Quality Index (DLQI) score at week 2, 4 and 8.
- Change from baseline in SCORAD at week 2, 4 and 8.
- Change from baseline in the patient's Visual Analog Scale (VAS) pruritus score at Week 2, 4 and 8.
- Change from baseline in Body Surface Area (BSA) at Week 2, 4 and 8.
- Number of treatment-emergent adverse events (TEAEs) in each treatment group.

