Analyses for the secondary endpoints will be done using observed data and no imputation will be used for missing observation.

All details regarding the statistical analyses will be included in a separate statistical analysis plan.

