Subjective items include loss of sleep and the occurrence of pruritus. These are evaluated by asking patients to indicate on the 10-cm scale (0-10) of the assessment form the point corresponding to the average value for the last three days/nights. The combined maximum score of these two is 20.

The sum of the above measures represents the SCORAD which can vary from 0 to 103. If the subjective scores of pruritus and loss of sleep are excluded, the SCORAD becomes objective SCORAD (score range 0-83)

22 APPENDIX E - Patient-Oriented Eczema Measure (POEM)

Patient ID #: _____ - _____

Patient Initials: _____

Visit Day: _____

Visit Date (dd-mmm-yyyy): _____

Please circle one response for each of the seven questions below about your eczema. Please leave blank any questions you feel unable to answer.

1. Over the last week, on how many days has your skin been itchy because of your eczema?

No days 1-2 days 3-4 days 5-6 days Every day

2. Over the last week, on how many nights has your sleep been disturbed because of your eczema?

No days 1-2 days 3-4 days 5-6 days Every day

3. Over the last week, on how many days has your skin been bleeding because of your eczema?

No days 1-2 days 3-4 days 5-6 days Every day

4. Over the last week, on how many days has your skin been weeping or oozing clear fluid because of your eczema?

No days 1-2 days 3-4 days 5-6 days Every day

5. Over the last week, on how many days has your skin been cracked because of your eczema?

No days 1-2 days 3-4 days 5-6 days Every day

6. Over the last week, on how many days has your skin been flaking off because of your eczema?

No days 1-2 days 3-4 days 5-6 days Every day

7. Over the last week, on how many days has your skin felt dry or rough because of your eczema?

No days 1-2 days 3-4 days 5-6 days Every day

© CR Charman, AJ Venn, HC Williams, December 2004.

23 APPENDIX F – Dermatology Life Quality Index (DLQI)

Patient ID #: _____ - _____

Patient Initials: _____

Visit Day: _____

Visit Date (dd-mmm-yyyy): _____

The aim of this questionnaire is to measure how much your skin problem has affected your life OVER THE LAST WEEK. Please check one box for each question.

1.	Over the last week, how itchy, sore, painful or stinging has your skin been?	Very much A lot A little Not at all	    	

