5.3 Missing Data/Multiple Observations

No imputation will be done for all population and all parameters, except for the primary endpoint. A supportive analysis using the last observation carried forward (LOCF) method will be performed on responder analysis (see section 7.1 for details).

In the event that two values were collected for the same visit, the scheduled assessment value will be retained in the analyses, unless otherwise specified (e.g. lab error). However, all values will be presented in the data listings. Laboratory values of '< X' or '> X' will be set to 'X' for the analysis.

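### The POEM form invites patients to leave items blank, but the SAP voids the whole POEM score for a single blank: avoidable precision loss on a secondary endpoint (minor)

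*SAP*

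**What the plan says.** - **The form.** The POEM questionnaire in Protocol Appendix E tells the patient: "Please leave blank any questions you feel unable to answer".
- **The scoring rule.** SAP 3.4.2.2 defines POEM as the sum of seven items, each rated 0 to 4, with a maximum of 28. It adds: "The score will be set to missing if there is at least one missing value".
- **The endpoint.** Protocol 3.2 lists as secondary: "Change from baseline in the Patient Orientated Eczema Measure (POEM) at week 2, 4 and 8". SAP 3.4.2.2 defines the change: "The change from Baseline will be calculated as the value at the visit minus the value at Baseline". SAP 7.2 analyses it by ANCOVA with the baseline value as covariate, and adds Week 10 and the change from Week 8 to Week 10.
- **Missing data.** SAP 5.3: "No imputation will be done for all population and all parameters, except for the primary endpoint". Protocol 14.2.2: "Analyses for the secondary endpoints will be done using observed data and no imputation will be used for missing observation". SAP 7.2 rules out any missing-data sensitivity analysis for the secondary endpoints.
- **The DLQI, for contrast.** Its form (Protocol Appendix F) asks the patient to check that every question is answered. SAP 3.4.2.2 nevertheless keeps the DLQI total when an item is unanswered, by scoring that item 0.
- **EASI.** SAP 3.4.2.2 has a similar any-missing rule: "The score will be set to missing in case of at least one missing value".

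**The concern.** The data collection form and the scoring rule pull against each other. On the form, a blank is a legitimate response; in the SAP, it destroys the total. The DLQI is treated the other way round: the form that asks for every answer tolerates blanks in scoring, while the form that permits blanks does not. The SAP gives no reason for the difference.

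At stake is the number of patients in the POEM comparison. A change score needs two complete forms, 14 answered items in all, so even a low blank rate per item can add up. Baseline matters most, because that score enters every change from baseline and is also the covariate.

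**Working it through.** **Inputs from the documents.** Seven items per form (SAP 3.4.2.2; 7 x 4 = 28 agrees with the stated maximum). Two forms per change score, hence 14 items. For scale, 90 patients attending both visits: SAP section 4 gives 45, read here as per arm, and 90/(1 - 0.10) = 100 matches the stated enrolment.

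**Input assumed.** The probability q that an item is blank, taken as 0.5%, 1% and 2%, independent across items and visits. The documents state no rate, so there is no plan figure to reproduce.

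**Formulas.**
- Visit score void: 1 - (1 - q)^7
- Change score void: m = 1 - (1 - q)^14
- Standard error inflation: sqrt(1/(1 - m)) - 1
- Change score void if one blank per form is tolerated: 1 - [(1 - q)^7 + 7q(1 - q)^6]^2

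For example, at q = 1%: 0.99^7 = 0.932, so 6.8% of visit scores are void; 0.99^14 = 0.869, so 13.1% of change scores are void; sqrt(1/0.869) = 1.073; 90 x 0.869 = 78 patients keep a change score.

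| q | Visit scores void | Change scores void | SE increase | Kept, of 90 | Void if one blank tolerated |
|---|---|---|---|---|---|
| 0.5% | 3.4% | 6.8% | 3.6% | 84 | 0.1% |
| 1% | 6.8% | 13.1% | 7.3% | 78 | 0.4% |
| 2% | 13.2% | 24.6% | 15.2% | 68 | 1.6% |

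**Sensitivity to independence.** Suppose each patient leaves the same items blank at both visits, with items still independent within a form. The second visit then adds no loss, and the change-score loss falls to the visit-score column: 3.4%, 6.8% and 13.2%. Clustering of blanks within a form would lower it further. It would also produce more forms with two or more blanks, which a one-blank tolerance does not rescue.

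**Which analyses lose the patient.**
- Blank at Week 2, 4 or 10: the change from baseline at that visit, plus the Week 8 to Week 10 change if the blank is at Week 10.
- Blank at Week 8: the Week 8 change from baseline and the Week 8 to Week 10 change.
- Blank at baseline: all changes from baseline (Weeks 2, 4, 8 and 10). The Week 8 to Week 10 difference can still be computed. SAP 7.2 does not say which covariate that model uses, so whether the patient stays in it is open.

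**Size of a pro-rating error.** Scoring the sum of six answered items times 7/6 fills the blank with the mean of the other six, a value between 0 and 4. The total can therefore differ from the true one by at most 4 of 28 points.

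**The case against.** **Complete-item scoring is a defensible choice.** It is explicit, pre-specified and reproducible, and the item answers remain in the listings (Listing 16.2.6.3). That is true, but listing the answers does not bring them into the analysis.

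**The size is unknown.** The blank rate and the independence are both assumptions, and independence probably overstates the loss. The questions concern the patient's own skin and sleep over the past week, so inability to answer may be rare. This stands, and it is the main reason for rating the point minor.

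**Sites could query blanks.** Protocol section 11 describes automatic eCRF checks. They may catch some blanks, but a POEM blank is permitted by the form, neither document describes a POEM-specific check, and a later query about the past week may not recover the answer.

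**Pro-rating is itself imputation.** It conflicts with SAP 5.3 and with Protocol 14.2.2, and the 7/6 rule has no source in the documents. This stands: the change must be declared as an exception, not slipped into the scoring text.

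**Stronger readings that a reader might infer.**
- *Patients drop out of the endpoint altogether.* Only a baseline blank removes every change from baseline; a later blank costs only the changes that use that visit.
- *The treatment comparison is biased.* The documents give no mechanism by which blanks would differ between blinded arms.
- *The EASI rule penalises the best responders, whose regions have cleared.* All four signs are to be scored in all four regions and 0 is an available score, so a cleared region has a valid entry. Nothing says that signs are left blank there. A region may also be uninvolved from the start, since entry requires only 10% body surface area.

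**Conclusion.** The inconsistency is real and follows from the texts alone: a patient who does what the POEM form says forfeits that visit's total, and no provision restores it. The consequence shown is avoidable loss of precision on one secondary endpoint. The figures of 6.8%, 13.1% and 24.6% of change scores, with standard errors up about 4%, 7% and 15%, are conditional on the assumed blank rates and on independence; they illustrate the loss and do not predict it. If blanks are very rare, the loss is negligible. The documents do not support a claim of bias between arms or of selective EASI loss. The primary IGA endpoint and the sample size are unaffected. Severity is minor, but the remedy is cheap and is best settled while the treatment codes are still blinded, because a partial-form rule chosen afterwards would be open to challenge.

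**What to change.** Before unblinding:

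1. **SAP 3.4.2.2 (POEM).** If exactly one of the seven items is blank, score the sum of the answered items x 7/6. If two or more are blank, set the score to missing.
2. **SAP 5.3.** State that this item-level scoring rule is an exception to the no-imputation rule.
3. **SAP section 11.** Record it as a departure from Protocol 14.2.2.
4. **Sensitivity analysis.** Repeat the POEM analyses with the complete-item score, and amend the sentence in SAP 7.2 that excludes missing-data sensitivity analyses accordingly.

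Optional, and free of assumptions: state that an EASI region with area score 0 contributes 0 even if one of its sign scores is blank. Each regional term is multiplied by its area score, so the term is exactly 0 whatever the signs.

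**Cost.** A few sentences in four places of the SAP and one extra set of POEM tables; data collection does not change. The downside is that pro-rating assumes the blank item resembles the patient's other items. The complete-item sensitivity analysis shows whether that matters.
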